11.1.4.3. Hepatic function abnormalities (hepatotoxicity)

Increased transaminases have been reported during treatment with anti-PD-L1/anti-PD-1 antibodies (Brahmer et al 2012). Inflammatory hepatitis has been reported in 3% to 9% of subjects treated with anti-CTLA-4 monoclonal antibodies (e.g., ipilimumab). The clinical manifestations of ipilimumab-treated subjects included general weakness, fatigue, nausea, and/or mild fever and increased liver function tests such as AST, ALT, alkaline phosphatase, and/or total bilirubin.

Hepatic function abnormality is defined as any increase in ALT or AST to greater than $3 \times ULN$ and concurrent increase in total bilirubin to be greater than $2 \times ULN$. Concurrent findings are those that derive from a single blood draw or from separate blood draws taken within 8 days of each other. Follow-up investigations and inquiries will be initiated promptly by the investigational site to determine whether the findings are reproducible and/or whether there is objective evidence that clearly supports causation by a disease (e.g., cholelithiasis and bile duct obstruction with distended gallbladder) or an agent other than the investigational product. Guidelines for management of subjects with hepatic function abnormality are outlined in Section 6.1.1.

Cases where a subject shows an AST or ALT $\geq 3 \times ULN$ or total bilirubin $\geq 2 \times ULN$ may need to be reported as SAEs, these cases should be reported as SAEs if, after evaluation, they meet the criteria for a Hy's Law case or if any of the individual liver test parameters fulfill any of the SAE criteria.

Criteria for Hy's Law (FDA Guidance 2009)

- The drug causes hepatocellular injury, generally shown by a higher incidence of 3-fold or greater elevations above the ULN of ALT or AST than the (non-hepatotoxic) control drug or placebo
- Among trial subjects showing such aminotransferase elevations, often with aminotransferases much greater than 3 x ULN, one or more also show elevation of serum total bilirubin to >2 x ULN, without initial findings of cholestasis (elevated serum alkaline phosphatase)
- No other reason can be found to explain the combination of increased aminotransferases and total bilirubin, such as viral hepatitis A, B, or C; pre-existing or acute liver disease; or another drug capable of causing the observed injury.

11.1.5. Unexpected Adverse Event:

An adverse event not mentioned in the Investigator's Brochure or Prescribing Information or the specificity or severity of which is not consistent with the Investigator's Brochure or Prescribing Information, or is not included in the informed consent document as a potential risk.

11.1.6. Related Adverse Event

There is a reasonable possibility the drug caused the adverse experience.

Unrelated	The Adverse Event is clearly not related to the investigational agent(s)
Unlikely	The Adverse Event is doubtfully related to the investigational agent(s)
Possible	The Adverse Event may be related to the investigational agent(s)

Probable	The Adverse Event is likely related to the investigational agent(s)	
Definite	The Adverse Event is clearly related to the investigational agent(s)	

11.2. Reporting

11.2.1. Adverse Events (AEs)

Adverse events (AEs) will be recorded from the time of consent and for at least 90 days after treatment discontinuation, regardless of whether or not the event(s) are considered related to trial medications. The descriptions and grading scales found in the revised NCI Common Terminology Criteria for Adverse Events (CTCAE) version 4 will be utilized for AE reporting. A copy of the current CTCAE version can be downloaded from the CTEP website at http://ctep.cancer.gov.

During the course of the study all AEs should be proactively followed up for each subject. The investigator is responsible for following all AEs until resolution, return to baseline status, or stabilization with the expectation that it will remain chronic, even if this extends beyond study drug administration.

11.2.2. Serious Adverse Events (SAE)

11.2.2.1. Site Requirements for Reporting SAEs:

Investigators and other site personnel must report all SAEs occurring during the course of the study within **one business day** of discovery of the event. This includes events both related and unrelated to the investigational product or to the study procedure(s). The reporting period for SAEs is the period immediately following the time that written informed consent is obtained through 90 days after the last dose of durvalumab or until the initiation of alternative anticancer therapy.

The completed SAE Submission Form (see Documents/Info tab of the EDC) must be sent electronically to [contact] at Big Ten Cancer Research Consortium (Big Ten CRC) Administrative Headquarters (AHQ) within one business day of discovery of the event. The investigator is responsible for informing the IRB and/or the Regulatory Authority of the SAE as per local requirements.

The original copy of the SAE Submission Form and the e-mail correspondence must be kept within the study file at the study site.

Follow-up information must be sent electronically to Big Ten CRC AHQ at [contact], using a new SAE Submission Form stating that this is a follow-up to the previously reported SAE and giving the date of the original report. Each re-occurrence, complication, or progression of the original event should be reported as a follow-up to that event regardless of when it occurs.

The follow-up information should describe:

- whether the event has resolved or continues,
- if and how it was treated,
- whether the subject continued or withdrew from study participation.

11.2.3. Big Ten CRC AHQ Requirements for Reporting SAEs:

11.2.3.1. Big Ten CRC AHQ Reporting to AstraZeneca/ MedImmune

Big Ten CRC AHQ will submit all FDA reportable SAEs to AstraZeneca within one business day of receipt of the SAE Submission Form from the site. Big Ten CRC AHQ will submit a MedWatch Form to AstraZeneca and will provide follow-up information as reasonably requested.

Serious adverse events that do not require expedited reporting to the FDA still need to be reported to AstraZeneca, preferably using the MedDRA coding language for serious adverse events. This information should be reported on a monthly basis and under no circumstance less frequently than quarterly.

Send SAE report and accompanying cover page by way of email to AstraZeneca's designated mailbox: [contact]

11.2.3.2. Big Ten CRC AHQ Reporting to the Food and Drug Administration (FDA)

Big Ten CRC AHQ will manage the Investigational New Drug Application (IND) associated with this protocol on behalf of [name]., Sponsor-investigator. Big Ten CRC AHQ will cross-reference this submission according to local regulations to the AstraZeneca Investigational Compound Number (IND, CSA, etc.) at the time of submission. Additionally, Big Ten CRC AHQ will submit a copy of these reports to AstraZeneca at the time of submission to FDA.

Big Ten CRC AHQ will be responsible for all communication with the FDA including but not limited to 7 and 15 Day Reports, as well as an Annual Progress Report. Big Ten CRC AHQ will report to the FDA, regardless of the site of occurrence, any AE that is serious, unexpected, and reasonably related (i.e., possible, probably, definite) to the study treatment. The sponsor-investigator will review these reports and determine if any revisions are needed to the protocol or consent.

7-Day Reports:

- Big Ten CRC AHQ will report unexpected fatal or life-threatening events associated with the use of the study treatment will be reported to the FDA.
- Big Ten CRC AHQ will report these events either by fax or by phone as soon as possible but in no event later than 7 calendar days after the initial receipt of the information regarding the event. The fax should be sent to the FDA project manager assigned to the IND. A comprehensive written report will be submitted as an amendment to the IND within an additional 8 days (15 calendar days, total).

15-Day Reports:

• Big Ten CRC AHQ will submit all other serious unexpected events associated with the use of the study treatment to FDA as an amendment to the IND as soon as possible but in no event later than 15 calendar days after initial receipt of the information regarding the event.

* A cover page should accompany the MedWatch form indicating the following:

- "Notification from an Investigator Sponsored Study"
- The investigator IND number assigned by the FDA

- The investigator's name and address
- The trial name/title and AstraZeneca ISS reference number (ESR-14-10654)

* Sponsor must also indicate, either in the SAE report or in the cover page, the causality of events in relation to all study medications and if the SAE is related to disease progression, as determined by the principal investigator.

Annual Progress Reports

• Big Ten CRC AHQ will submit an annual progress report within 60 days of the anniversary of the date that the IND went into effect.

11.2.4. Other events requiring immediate reporting

11.2.4.1. Requirements for Reporting Overdose

An overdose is defined as a subject receiving a dose of durvalumab in excess of that specified in the Investigator's Brochure, unless otherwise specified in this protocol.

Any overdose of a study subject with durvalumab, with or without associated AEs/SAEs, is required to be reported to Big Ten CRC AHQ within 24 hours of knowledge of the event. Big Ten CRC AHQ will report the event to AstraZeneca/MedImmune Patient Safety or designee within 24 hours using the designated Safety e-mailbox. If the overdose results in an AE, the AE must also be recorded as an AE. Overdose does not automatically make an AE serious, but if the consequences of the overdose are serious, for example death or hospitalization, the event is serious and must be recorded and reported as an SAE. There is currently no specific treatment in the event of an overdose of durvalumab.

The investigator will use clinical judgment to treat any overdose.

11.2.4.2. Requirements for Reporting Hepatic function abnormality

Hepatic function abnormality (as defined in Section 11.1.4.3) in a study subject, with or without associated clinical manifestations, is required to be reported as "hepatic function abnormal" *within 24 hours of knowledge of the event* to Big Ten CRC AHQ, unless a definitive underlying diagnosis for the abnormality (e.g., cholelithiasis or bile duct obstruction) that is unrelated to investigational product has been confirmed. Big Ten CRC AHQ will report the event to AstraZeneca/MedImmune Patient Safety or designee within 24 hours using the designated Safety e-mailbox.

- If the definitive underlying diagnosis for the abnormality has been established and is unrelated to investigational product, the decision to continue dosing of the study subject will be based on the clinical judgment of the site investigator.
- If no definitive underlying diagnosis for the abnormality is established, dosing of the study subject must be interrupted immediately. Follow-up investigations and inquiries must be initiated by the investigational site without delay.

Each reported event of hepatic function abnormality will be followed by the site investigator and evaluated by the sponsor-investigator and AstraZeneca/MedImmune.

11.2.4.3. Requirements for Reporting Pregnancy

Pregnancy itself, or pregnancy of a subject's partner, is not regarded as an adverse event unless there is a suspicion that the investigational product under study may have interfered with the effectiveness of a contraceptive medication. Congenital abnormalities/birth defects and spontaneous miscarriages should be reported and handled as SAEs. Elective abortions without complications should not be handled as AEs. The outcome of any conception occurring from the date of the first dose until 90 days after the last dose (spontaneous miscarriage, elective termination, ectopic pregnancy, normal birth, or congenital abnormality) should be followed up and documented even if the subject was withdrawn from the study drug.

Pregnancy in a female subject who has received investigational product is required to be reported *within 24 hours of knowledge of the event* to Big Ten CRC AHQ on the Pregnancy Report form (See Documents/Info tab of the EDC). Big Ten CRC AHQ will report the event to AstraZeneca/MedImmune Patient Safety or designee within 24 hours using the designated Safety e-mailbox.

Subjects who become pregnant during the study period must not receive additional doses of investigational product but will not be withdrawn from the study. The pregnancy will be followed for outcome of the mother and child (including any premature terminations) and should be reported to Big Ten CRC AHQ after outcome. Big Ten CRC AHQ will report the event to AstraZeneca/MedImmune Patient Safety or designee within 24 hours using the designated Safety e-mailbox.

Male subjects should refrain from fathering a child or donating sperm during the study and for 3 months following the last dose.

Should the investigator become aware of a pregnancy in the partner of a male study subject who has received investigational product this should be reported *within 24 hours of knowledge of the event* to Big Ten CRC AHQ on the Pregnancy Report form (See Documents/Info tab of the EDC). The site investigator will endeavor to collect follow-up information on such pregnancies provided the partner of the study subject provides consent.

11.3. IND Safety Reports Unrelated to This Trial

IND safety reports not occurring on this trial but involving the study intervention (outside SAEs) received from outside sources will be forwarded to participating sites for submission to their Institutional Review Boards per their guidelines. The sponsor-investigator will review these reports and determine if any revisions are needed to the protocol or consent.

12. STATISTICAL CONSIDERATIONS

12.1. General Considerations

Statistical analysis of this study will be the responsibility of Biostatistics and Data Management Core at Indiana University Melvin and Bren Simon Cancer Center (IUSCC). Parameter estimates and relevant summary statistics will be reported where appropriate. For continuous variables, summary statistics will include number of subjects, mean, median, standard deviation, minimum and maximum. Categorical endpoints will be summarized using number of subjects, frequency, and percentages. Missing data will not be imputed. Data analysis will be performed in SAS Version 9.4.

Additional exploratory analyses of the data will be conducted as deemed appropriate. Changes from this analysis plan will not require an amendment to the protocol unless it changes a significant feature of the protocol.

12.2. Study Design

This is an open label single-arm single-stage phase II trial.

12.3. Definition of Primary Endpoint

- Relapse free survival: Time from the date of surgery until the criteria for disease relapse is met or death occurs.
- One year relapse free survival: Subject is alive and relapse free at one year post-surgery.

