	 After six patients are treated with at least one dose of study drug, they will be observed for a minimum of 60 days. During the 60-day observation period, further accrual will be halted to evaluate "unacceptable toxicities warranting early closure of the trial" defined as: 1) Any definitive durvalumab-related death. A durvalumab-related death will be continuously monitored throughout the trial and the trial will be suspended for re-evaluation whenever such an event is confirmed. 2) Any unexpected and previously unreported grade 4 toxicities definitely related to durvalumab. 		
	If such events are observed in one subject, the DSMB will discuss and provide recommendations to the sponsor-investigator. If such events are observed in two or more subjects, the trial will be suspended for re- evaluation.		
	Pneumonitis of grade 3 and 4 will be continuously monitored. An overall rate of 20% or above would be considered unacceptable. If the probability of the grade 3/4 pneumonitis rate being less than 20% drops below 0.1, the trial will be suspended for re-evaluation.		
ELIGIBILITY CRITERIA	 Inclusion Criteria: Esophageal cancer with persistent residual disease in the surgical sample following neoadjuvant concurrent chemoradiotherapy (carboplatin and paclitaxel or cisplatin and 5-FU) followed by surgical resection. Must have had R0 resection (defined as resection with negative margins) Minimum of 1 month and maximum of 3 months from surgical resection with no evidence of disease recurrence at the time of enrollment ECOG Performance status 0-1 Adequate bone marrow, renal and hepatic function Must have adequately recovered from chemoradiation and surgery Exclusion Criteria: Prior therapy with a PD-1, PD-L1, or CTLA-4 inhibitor or cancerspecific vaccine therapy Patients with R1 resection (defined as positive margins after resection) or R2 resection (defined as presence of macroscopic residual disease after resection) Evidence of active autoimmune disease requiring systemic treatment within preceding 3 months or a documented history of clinically severe autoimmune disease, or a syndrome that requires ongoing use of systemic steroids or immunosuppressive agents. Exceptions to this rule include vitiligo, resolved childhood asthma/atopy, requirement of intermittent bronchodilators or local steroid injections, hypothyroidism stable on hormone replacement, Sjogren's syndrome. 		

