3. ELIGIBILITY CRITERIA

3.1.Inclusion Criteria

Subject must meet all of the following applicable inclusion criteria to participate in this study:

3.1.1 Written informed consent and HIPAA authorization for release of protected health information obtained from the subject prior to performing any protocol-related procedures, including screening evaluations.
 NOTE: HIPAA authorization may be included in the informed consent or obtained

NOTE: HIPAA authorization may be included in the informed consent or obtained separately.

- **3.1.2** Age \geq 18 years at the time of consent.
- **3.1.3** ECOG Performance Status of 0-1 within 28 days prior to registration for protocol therapy.
- **3.1.4** Females of childbearing potential and males must be willing to use two effective methods of contraception (See section 5.5.1) from the time consent is signed until 3 months after treatment discontinuation.
- **3.1.5** Females of childbearing potential must have a negative serum pregnancy test within 14 days prior to registration for protocol therapy.

NOTE: Female subjects are considered of childbearing potential unless they are surgically sterile (they have undergone a hysterectomy, bilateral tubal ligation, or bilateral oophorectomy) or they are ≥ 60 years old and naturally postmenopausal for at least 12 consecutive months. See section 5.5.1.

- 3.1.6 Histological evidence of persistent residual esophageal adenocarcinoma including gastroesophageal junction adenocarcinoma following definitive concurrent chemoradiotherapy (carboplatin and paclitaxel or cisplatin and 5-FU) in the surgical sample (esophagus or lymph node or both) obtained at the time of esophagectomy.
 NOTE: Persistent residual disease is defined as follows (modified from College of American Pathologists Guidelines):
 - No residual tumor (Grade 0, complete response, 0% tumor). This group will not be included in this study.
 - Marked response (Grade 1, 0-<10% residual tumor)
 - Moderate response (Grade 2, 10-50% residual tumor)
 - No definite response (Grade 3, >50% residual tumor)
- **3.1.7** Minimum of 1 month and maximum of 3 months from surgical resection with no evidence of disease progression at the time of enrollment.
- 3.1.8 Must have adequately recovered from surgery as judged by the treating investigator.
- **3.1.9** Laboratory values must be obtained within 28 days prior to registration for protocol therapy.

- White blood cell count (WBC) \geq 3 K/mm³

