Historical outcomes of patients who receive chemoradiotherapy followed by surgical resection and are noted to have persistent disease at the time of surgery are poor with 50% of them recurring in the first year (34). We expect durvalumab to improve the relapse free survival at 1 year rate by 25%. The null hypothesis is that 1 year RFS with postoperative adjuvant durvalumab therapy in patients with persistent esophageal cancer following neoadjuvant chemoradiotherapy and esophagectomy is 50% or less. Alternative hypothesis is that 1 year RFS with postoperative adjuvant durvalumab therapy in patients with persistent esophageal cancer following neoadjuvant chemoradiotherapy and esophagectomy is 75% or greater. With a maximum acceptable type I error (the probability of concluding that the drug is effective when it is actually not effective) of 0.05, and acceptable type II error (the probability of concluding that the drug is not effective when it is actually effective) of 0.20, the calculated sample size is 23 evaluable patients. If the total number of patients free of relapse at 1 year is less than or equal to 15, the drug would not be considered for further study. Up to 26 will be enrolled to allow for 10% unevaluable for efficacy. Subjects who receive less than 6 months of durvalumab for reasons unrelated to disease progression or toxicity will be replaced. Estimated accrual period is 18 months; follow up period of 12 months. To improve accuracy for estimating the primary endpoint (1 year RFS) with a 95% confidence interval, an additional 11-16 patients beyond the initial planned 23 evaluable will be enrolled for a target of 39 enrolled and at least 34 patients evaluable for 1 year RFS (to allow for approximately 10% unevaluable). With n=34 evaluable, if the 1 year RFS is 75%, a 95% two-sided confidence interval will have a half-width of 15% (using normal-approximation).

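### One-year RFS runs from surgery in patients already event-free 1 to 3 months later, but the historical 50% carries no such condition, so the 5% type I error is not assured

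*Combined protocol and SAP*

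**What the plan says.** - **Clock.** Sections 8.1.3 and 12.3 start RFS at the date of surgery and count relapse or death. The one-year endpoint is "One year relapse free survival: Subject is alive and relapse free at one year post-surgery".
- **Entry.** Section 3.1.7 requires "Minimum of 1 month and maximum of 3 months from surgical resection with no evidence of disease progression at the time of enrollment"; the synopsis has the same window with recurrence in place of progression. The efficacy-evaluable set (12.8) also requires at least one dose.
- **Benchmark.** Section 12.6 says that historical patients who "are noted to have persistent disease at the time of surgery are poor with 50% of them recurring in the first year". The null is set at 50% or less and the alternative at 75% or more, both as one-year RFS.
- **Decision rule.** "If the total number of patients free of relapse at 1 year is less than or equal to 15", the drug is not taken further. This belongs to the 23-patient calculation, with type I error 0.05 and type II error 0.20.
- **Expansion and primary analysis.** The target is now at least 34 evaluable, justified by precision: "With n=34 evaluable, if the 1 year RFS is 75%, a 95% two-sided confidence interval will have a half-width of 15% (using normal-approximation". Section 12.12 makes the primary analysis an estimate of one-year RFS with a 95% confidence interval, plus a Kaplan-Meier curve. Sections 12.6, 12.12 and 12.14 describe no landmark, delayed-entry or conditional adjustment.

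**The concern.** The trial has one arm, and its primary objective is improvement over historical rates, so the 50% acts as the control group. Up to a quarter of each patient's 12-month window (3 of 12 months) has passed before that patient can enter, and an event detected in that time keeps the patient out. If the historical group was followed from surgery without the same filter, its early failures count against it, while the trial's equivalents are never enrolled. Reaching 16 of 23, or obtaining a confidence interval above 50%, could then partly reflect who was enrolled rather than what the drug did. Section 12.6 describes type I error as declaring an ineffective drug effective, so this bears directly on the stated 5%.

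**Working it through.** **Inputs.** From 12.6: null 0.50, alternative 0.75, n = 23, success at 16 or more, 34 evaluable after expansion. From 3.1.7: entry at month m = 1 to 3. The documents give no hazard shape and no early event rate, so steps 3 to 6 rest on assumptions.

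**1. Reproduce the plan.** With X ~ Binomial(23, p):
- P(X ≥ 16 | 0.50) = 0.0466
- P(X ≥ 16 | 0.75) = 0.804

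The design is correct, read as one-sided, if the no-effect rate is exactly 50%. The expansion's precision also reproduces: 1.96 × √(0.75 × 0.25 / 34) = 0.146, or about 15%.

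**2. Slack in the rule.** P(X ≥ 16 | p) reaches 0.05 at p = 0.5036. If 0.50 is unconditional RFS from surgery and a fraction f fails before entry, the no-effect rate in enrollable patients is 0.50 / (1 − f). The slack is used up at f = 1 − 0.50/0.5036 = 0.7%. With f = 5% the rate is 0.526 and alpha 0.077. With f = 10% the rate is 0.556 and alpha 0.126.

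**3. Constant hazard (illustration).** S(m) = 0.50^(m/12), and the conditional no-effect rate is p = 0.50 / S(m).

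| Entry month | S(m) | p | P(X ≥ 16 of 23) |
|---|---|---|---|
| 1 | 0.944 | 0.530 | 0.082 |
| 2 | 0.891 | 0.561 | 0.138 |
| 3 | 0.841 | 0.595 | 0.221 |

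**4. The interval from 34 evaluable, read against 50%.** The normal-approximation lower limit is 0.486 at 22/34 and 0.519 at 23/34, so the interval clears 50% from 23. The exact lower limit is 0.495 at 23/34 and 0.525 at 24/34, so it clears 50% from 24.

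| No-effect rate | Normal approximation, P(X ≥ 23 of 34) | Exact, P(X ≥ 24 of 34) |
|---|---|---|
| 0.500 | 0.029 | 0.012 |
| 0.530 | 0.060 | 0.028 |
| 0.561 | 0.118 | 0.062 |
| 0.595 | 0.214 | 0.125 |

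**5. Other hazard shapes.** Take Weibull S(m) = 0.50^((m/12)^k) with entry uniform over months 1 to 3. Shape k = 2 (few early events) gives p = 0.511 and alpha 0.057 for the 16-of-23 rule. Shape k = 0.7 (many early events) gives p = 0.609 and alpha 0.26.

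**6. What would cancel it.** Suppose historical RFS from surgery, once relapse-free deaths are counted, was below 50%. Under uniform entry the conditional no-effect rate returns to 0.50 if that figure was about 0.489 (k = 2), 0.435 (constant hazard) or 0.380 (k = 0.7). If the conditional rate were 0.45, alpha would be 0.015, well under nominal.

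**The case against.** - **The null has a clock.** A reader might infer that the null has no time origin. The documents do not support that: 12.6 states it as one-year RFS, which 12.3 runs from surgery. Only the historical figure lacks an explicit start, and its wording about disease at the time of surgery points to surgery. This stands.
- **The direction is not established.** The 50% counts recurrences. Deaths without relapse would lower the comparable RFS, and the cited source may already be restricted to patients event-free after surgery. This stands, and it rules out a claim that the error rate is inflated. It does not show that the benchmark matches the endpoint.
- **The 16-of-23 rule belongs to the original sample.** The current primary analysis is an interval from at least 34, and reading it against 50% is a use the plan does not prescribe. With an exact interval the no-effect probabilities are smaller than for the 23-patient rule. This stands as to size, but the objective is still a comparison with historical rates and 50% is the only rate given.
- **Entry needs only no evidence of progression.** A reader might infer that no relapse arising before entry can ever count. That goes too far: the baseline CT may be up to 28 days before registration (7.1.1), and an occult relapse can be detected later and counted. Deaths and detected relapses are what the entry rule removes.

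**Conclusion.** The point holds in a limited form. The text establishes that the analysed patients are selected as event-free at entry, and that the historical 50% is not shown to share that condition, the endpoint's event definition or its start. The 5% is therefore not assured, because the 16-of-23 rule has almost no slack.

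The size is not established. The constant-hazard range of 0.08 to 0.22, and the wider Weibull range, assume that 50% is unconditional RFS at 12 months from surgery. A reader might infer that the trial's true type I error is about 14%, or that the 23-patient calculation is wrong. Neither follows: the calculation is right at 50%, and the net excess depends on a historical figure that the documents do not give and could be nil. This should be fixed, with moderate confidence; the mismatch is clear and only its net effect is open.

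**What to change.** **Change.** In 12.6, keep surgery as time zero and replace the 50% with the historical rate of being alive and relapse-free at 12 months among patients event-free at 1 to 3 months, taken from the source that 12.6 cites. Put the alternative on the same basis and restate type I error and power.

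**Until that rate is obtained:**
- State in 12.6 that the 5% holds only if no-effect RFS in enrollable patients is at most about 50%, and tabulate alpha over a range such as 50% to 60%. For 16 of 23, P(X ≥ 16) is 0.047 at 50%, 0.115 at 55% and 0.237 at 60%.
- In 12.12, describe the one-year estimate, its interval and the Kaplan-Meier curve as conditional on being event-free at entry, so that the interval is not read against an unconditional 50%.

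**Cost.** Extraction of one historical rate, one recalculation and some wording; no extra visits or scans. Changing the null alters a significant feature, so it needs an amendment (12.1, 14.4). The benchmark will probably be higher and the result will look less favourable. With the target held at 75% and illustrative nulls of 53%, 56% and 59%, cutoffs of 24, 25 and 26 of 34 keep one-sided alpha at about 0.03. Power, P(X ≥ cutoff | 34, 0.75), is then 79%, 66% and 51%. That loss should be reported rather than met by enrolling more patients. These nulls and cutoffs are illustrations, not replacement values.

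Starting RFS at registration or adding a delayed-entry estimate is optional. The absence of a decision cutoff for 34 patients is a separate point.
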